- (2) In subjects without ACS, first dose of atorvastatin is determined based on subjects' LDL-C levels at screening visit. The adjusted LDL-C level can be calculated based on the type of statin and dosage that subject is currently taking. If LDL-C \geq 110 mg/dl, atorvastatin 40 mg daily will be initiated. If LDL-C < 110 mg/dl, atorvastatin 20 mg daily will be initiated.

The treatment target for LDL-C will be \leq 80 mg/dl for the single and double therapy groups and \leq 60 mg/dl for the triple therapy group. In order to reach the LDL-C target, atorvastatin titration during the study will be conducted as followings:

- (1) Titration up: At 3 month follow-up visit, a blood sample is taken and LDL-C assessed. If subject's LDL-C did not reach the predefined target of \leq 80 mg/dl for single and double therapy groups or \leq 60 mg/dl for the triple therapy group, the atorvastatin dose will double. This process will be repeated at 5, 8 and 12 months and every 4 months after through out the study. 80mg atorvastatin is the highest possible dose that will be administered.
- (2) Titration down: At 3 month follow-up visit, a blood sample will be taken and LDL-C assessed. If subject's LDL-C < 40 mg/dl and > 25 mg/dl with normal AST/ALT lab values and does not report nausea or fatigue, careful monitoring will be conducted. No change will be made in the atorvastatin dosage. If subject has symptoms of fatigue and/or nausea and/or AST/ALT elevation per safety protocol, atorvastatin will be halved or stopped depending on the decision of the investigator. If subject's LDL-C < 25 mg/dl and no symptoms or liver enzyme elevation, atorvastatin will be halved. If subject has symptoms or AST/ALT elevation per safety protocol, atorvastatin will be stopped. This process will be repeated at 5, 8 and 12 months and every 4 months after throughout the study.

B.7. Niacin Dosing Up Schedule

Based on our 20 years of experience of using niacin in our previous studies, we designed a dosing-up schedule to help subjects to build the niacin tolerance and to better handle the side effects. This will also help to define a tolerable dose for each subject.

Medication initiation: take 500 mg, 1 tablet, with dinner daily.

1-month F/U visit: take 1000 mg, 2 tablets, with breakfast and dinner daily.

2-month F/U visit: take 1500 mg, 3 tablets, 1 at breakfast and 2 with dinner daily.

[figure not shown]
3-month F/U visit: take 2000 mg, 4 tablets, 2 with breakfast and 2 with dinner daily.

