This dosing-up can last as long as 6 months based on how well the subjects can tolerate each dosage level.

Aspirin (81-325mg) is recommended 30 minutes before taking niacin.

B.8. Study Medication Information and Instruction

In addition to the medication information listed in the study informed consent form, we will also provide subjects a separate document as shown below with the drug

information for the 3 medications used in CPC. **Pertinent Medication Information for the Carotid Plaque Composition by MRI During Lipid-lowering Study**

There are three study medications used in this study.

1. Lipitor (atorvastatin)

A member of the drug class known as statins, used for lowering cholesterol. Lipitor helps decrease the amount of LDL or ‘bad’ cholesterol in the blood by blocking an enzyme called HMG-CoA reductase, an enzyme that makes cholesterol. Statins reduce total cholesterol, as well as LDL-cholesterol, in the blood, which slows the progression of heart disease. Lipitor is generally well tolerated. In less than 1% of people, it may cause muscle aches or certain abnormalities of muscle-related blood tests. These problems are rare and are reversible by stopping the medication. In the study, blood sugar, liver function and muscle tests are taken often.

2. Slo-Niacin (slow-release niacin)

Slo-niacin is a medication used to raise levels of HDL or ‘good’ cholesterol and lower triglycerides. The risks from Slo-Niacin include a warm flushing sensation that occurs shortly after taking the medication, which may be difficult to tolerate. Slo-niacin may uncommonly (2-4% of users) cause a skin rash, increased blood sugar or cause mildly abnormal liver tests. Fatigue, nausea, loss of appetite and muscle aches may be drug-associated side effects, although generally rare.

3. Zetia (ezetimibe)

Ezetimibe works by preventing cholesterol absorption in the intestine. It is generally well tolerated. Side effects may include headache, dizziness, diarrhea, sore throat, runny nose, sneezing and joint pain. Rare side effects include hives, rash, itching or swelling, hoarseness, upset stomach, tiredness, unusual bleeding, pain, flu-like symptoms, muscle pain or weakness or chest pain.

The medication instruction sheet as shown below is also provided to all subjects at the study medication initiation visit.

Directions for CPC Study Medication Schedule

Morning Dosing Directions (AM):

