Take One ezetimibe pill and 1-2 pills of Slo-niacin (or half of the daily dose indicated on the bottle) as instructed, with breakfast.

Evening/Night Dosing Directions (PM):

Take 1-2 Atorvastatin pills with dinner, as indicated on the bottle. Take 1-2 pills of Slo-niacin (or half of the daily dose indicated on the bottle) with dinner or before bed.

Valuable Information:

Niacin can sometimes cause a flushing feeling when you first start taking it. If this occurs, there are a few suggestions to help stop or reduce this feeling. The flushing feeling usually goes away over time if you continue to take niacin.

Some helpful ideas for reducing niacin-related flushing:

1. Take your medication in the morning and right before bed.
2. If you use a daily aspirin, take it 30 minutes before your niacin (either morning or evening). Do not take more than 325 mg Aspirin daily without first talking to your doctor.
3. 'Flushing' is reduced by food in your stomach. Enjoy a low-fat snack before you take niacin. An ounce of cheese with a few crackers, a cup of milk or yogurt with fresh fruit are a few examples.
4. Avoid hot drinks, alcohol and spicy foods with dinner as this can sometimes encourage flushing from niacin.

The study medication dispensing process is described under B.11.

B.9. Clinical and Laboratory Follow-up Procedures:

After randomization, the study subjects will be seen monthly for six months and bi-monthly for the remaining 30 months of the 36-month protocol. A total of 22 visits will be conducted for this study as shown in the procedure table below. This clinic visit protocol is developed based on the successful FATS and HATS (RO1 HL49546) clinic visit models. The clinical visits will be done by a team of investigators, coordinators and nurses as well at each of 3 study sites.

Participants who complete the first 3 years of the study and are willing to continue on the randomized therapy and will be followed every 4 months for up to 11 more years.

Table. Clinical Follow-up Protocol

Visit	Entry Criteria	Con-sent	Med. Hx	Family Hx	Vital Signs	Diet Counseling	AE/ Side Effects	Drug Disp.	Com-pliance	Safety Moni-toring	Meds Adj.
Screening	X	X			X						
Baseline		X	X	X	X	X		X			
Non-blood draw visits*					X	X	X	X	X	X	X
Blood draw visits**					X	X	X		X	X	

*: C1, 2, 4, 6, 10, 14, then every 4 months up to C130. **: C3, 5, 8, 12, then every 4 months up to C132.

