All three medications are FDA approved drugs. Pfizer, Upsher-Smith, and Merck, Sharp and Dohme Corp are the three companies providing the medications (atorvastatin, Niacin, and ezetimibe). A drug supply record on each medication keeps tracking the quantity requested and received. All medication is stored at Harborview Investigational Drug Services (HMCIDS), as well as all documentation of drug dispensing.

With instruction from the UWMC Investigational Drug Services and Harborview Investigational drug Services, a study medication dispensing procedure has been developed as following.

(1) A medication card as shown below with the study name, drug information, and emergency contact information will be provided to each enrolled subject at the study medication initiation visit and repeat on their annual visits.

Study Name: Carotid Plaque Composition
Study Investigator: [name] [contact])
Study Coordinator: [name]
1. Lipitor (atorvastatin): 10-80mg/day

2. Slo-niacin (niacin): 1.5-2g/day
3. Zetia (erxetimibe) 10 mg/day

(2) The medication bottles/kits will be labeled with (a) study name, (b) subject name, (c) subject Harborview ID number, (d) medication name, (e) dispensing date, (f) expiration date, (g) total quantity, (h) instruction, and (i) a federal statement limiting use to the given study.

(3) For each enrolled subject at each scheduled study visit, a study medication prescription which is signed by the study doctor will be generated from our computer system based on the randomization, atorvastatin dosage determination and niacin dosing-up schedule, and duration between visits.

(4) Prescription requests are delivered to HMCIDS prior to the study visit and are then dispensed by HMCIDS.

(5) Each medication dispensing record will be saved in the subject medication folder.

(6) Medications will be dispensed to subjects in person at the end of each scheduled visit. All medication information and instruction will be reviewed with the subject at time of dispensing by an investigator.

(7) Subjects will receive two pill organizers, one for ezetimibe and niacin taken in the morning and one for atorvastatin and niacin at bed time, to help them to remember to take the study medications. We will also recommend placing the morning pill organizer in the kitchen and the night pill organizer maybe in the bathroom, this will help subjects to link the medication taking with their routine activities for optimal compliance.

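### The dosing sheet handed out at medication initiation directs niacin at breakfast, but the starting step in B.7 is one 500 mg tablet with dinner and none at breakfast (niacin arms only, low severity)

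*Combined protocol and SAP*

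**What the plan says.** Section B.7 (Niacin Dosing Up Schedule) opens with "Medication initiation: take 500 mg, 1 tablet, with dinner daily". Breakfast niacin begins at the 1-month visit, when the dose becomes two tablets taken at breakfast and dinner. The next step is "2-month F/U visit: take 1500 mg, 3 tablets, 1 at breakfast and 2 with dinner daily", and the last, at 3 months, is two tablets at each meal. The pace may be slower: "This dosing-up can last as long as 6 months based on how well the subjects can tolerate each dosage level".

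Section B.8 reproduces a take-home sheet (Directions for CPC Study Medication Schedule), which is "also provided to all subjects at the study medication initiation visit". Its morning line reads "Take One ezetimibe pill and 1-2 pills of Slo-niacin (or half of the daily dose indicated on the bottle) as instructed, with breakfast". Its evening niacin line reads "Take 1-2 pills of Slo-niacin (or half of the daily dose indicated on the bottle) with dinner or before bed". Among the tips for reducing flushing, the first is "Take your medication in the morning and right before bed". The sheet has no separate line for the starting step.

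**The concern.** The sheet is issued at the visit when the dinner-only step begins, and it tells the patient to take niacin at breakfast. B.7 explains that the gradual schedule is meant to build tolerance and to find a dose each subject can manage. The sheet itself warns that flushing can occur when niacin is first started. The conflict therefore falls at the step where the protocol intends the lowest exposure.

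What is at stake is the consistency of a patient instruction and, at worst, avoidable early side effects in the double and triple therapy groups. Nothing in the endpoints, sample size or analysis depends on it.

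**Working it through.** **Inputs.** Tablet strength is 500 mg at every step of B.7 (500 mg as 1 tablet, 1000 as 2, 1500 as 3, 2000 as 4). Tablets per meal come from B.7. The 1-month step does not give the split, so I read it as one tablet at each meal. The sheet's two wordings come from B.8: a pill count of 1 to 2 in the morning and 1 to 2 in the evening, or half of the bottle's daily dose each time.

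**Step-by-step comparison (morning + evening tablets).**

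| B.7 step | B.7 tablets | Fits the pill counts, (1–2) + (1–2)? | Half-dose wording | Fits? |
|---|---|---|---|---|
| Initiation, 500 mg | 0 + 1 | No (morning minimum is 1) | 0.5 + 0.5 | No |
| 1 month, 1000 mg | 1 + 1 | Yes | 1 + 1 | Yes |
| 2 months, 1500 mg | 1 + 2 | Yes | 1.5 + 1.5 | No |
| 3 months, 2000 mg | 2 + 2 | Yes | 2 + 2 | Yes |

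The pill counts fit 3 of 4 steps and the half-dose wording fits 2 of 4. Only the initiation step fits neither. The half-dose wording also misses the 1500 mg step, but there the pill counts cover it.

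**Daily dose at initiation if the sheet were followed literally.**

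- Pill counts, both lines: minimum (1 + 1) × 500 = 1000 mg; maximum (2 + 2) × 500 = 2000 mg. Against 500 mg: 1000/500 = 2 and 2000/500 = 4.
- Pill counts in the morning with the evening dose kept at one tablet, as B.7 has it: (1 + 1) × 500 = 1000 mg to (2 + 1) × 500 = 1500 mg. Against 500 mg: 2 to 3 times.
- Half-dose wording: 250 + 250 = 500 mg, ratio 1.0. The total is right, but half is moved to breakfast, which means splitting a tablet of a product that B.8 describes as slow-release.

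**Where the conflict sits.** The evening line can be read to fit the starting step (one pill with dinner). The morning line cannot under either wording. The first flushing tip also points to a morning dose, though it gives no amount.

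**The case against.** The best defence is that the sheet is a generic template and is not meant to stand alone. It goes to all subjects, including the single therapy group, who receive neither niacin nor ezetimibe, so it can only work alongside individual instructions. The morning line says the dose is taken as instructed and points to the bottle. A range of one to two pills cannot be followed without more specific direction. Read together with the half-dose parenthesis, the total stays at the bottle's daily dose, so the 2-to-4-fold figure requires ignoring the bottle that the sentence cites.

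There are also real safeguards. Under B.10, prescriptions are generated "based on the randomization, atorvastatin dosage determination and niacin dosing-up schedule, and duration between visits", the bottle carries an instruction and a total quantity, and an investigator goes through the instructions in person at dispensing. Unused tablets come back for compliance calculation. If step 1 were supplied as about 30 tablets with no overage (an assumption; the protocol gives no quantity), taking 2 to 4 a day would exhaust them in 30/4 = 7.5 to 30/2 = 15 days. Under C.3, severe symptoms reported at the 1-month visit go to the safety monitor.

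Much of this stands. Misdosing is unlikely, and the ratios are literal readings, not expected errors. The flushing tip is weak evidence, since it is optional advice. But deferring to other instructions does not state the exception, and the words around that deferral still name at least one pill, or half the dose, at breakfast. Even the reading that keeps the total at 500 mg contradicts B.7 on timing. The safeguards lower the chance that a patient acts on the error; they do not make the sheet correct, and the sheet is what the patient takes home after the review.

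**Conclusion.** The sheet is wrong as written at the starting step; the severity is low. It affects one of four steps, lasting about the first month (longer if tolerance is slow), in the two niacin groups out of three. A literal reading gives between 1.0 and 4 times the intended 500 mg/day, depending on which wording is followed. Every reading puts niacin at breakfast, where B.7 has none.

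This rests on the sheet being handed out at initiation, as B.8 states, and on taking its words at face value. The protocol does not reproduce the bottle instruction, so what patients actually read there is unknown. This protocol version covers the extension, so few new niacin starts may remain; the documents do not say.

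**What to change.** Add one line to the sheet: *While you are on one niacin tablet a day, take it with dinner and none at breakfast.* Tying the line to the dose, and not to the calendar, keeps it right when the first step lasts longer than a month.

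Alternatively, drop the niacin pill counts and the half-dose wording and direct patients to the number of tablets per meal on the bottle label. This would also remove the mismatch between the half-dose wording and the 1500 mg step. It works only if the label gives tablets per meal, which B.10 does not confirm, so the added line is the safer choice.

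In either case, reword the first flushing tip to match, and mark the niacin and ezetimibe lines as applying only if assigned. The cost is a template edit to one sheet and IRB approval of the revision.

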(4) To investigate the effects of HDL-raising and very intensive LDL-lowering on carotid plaque characteristics over 3 years. To achieve this goal, we will (a) perform quantitative assessment of plaque lipid, volume, and enhancement at all 4 time points blinded to the MRI time sequence and treatment; (b) compare the change in plaque characteristics over 3 years between single and double therapy for HDL-raising effect, between double and triple therapy for more intensive LDL-lowering effect, and single and triple therapy for more LDL-lowering plus HDL-raising effect.

(5) To determine if carotid plaque characteristics predict future major cardiovascular events. To achieve this goal, we will (a) continue to conduct clinical follow-up for a median of 5 years to collect cardiovascular events including fatal/non-fatal MI or stroke, hospitalization/revascularization for worsening ischemia, and mortality; (b) determine whether plaque characteristics (lipid content, volume and enhancement) at baseline and its change during therapy are statistically associated with cardiovascular events.

[figure not shown]
This study employs the state-of-the-art technique to assess both the magnitude and mechanisms of benefit of lipid therapy. It will be one of the first studies to examine the effects of lipid-lowering therapy on human atherosclerotic plaques in vivo and will provide novel insights into our understanding of atherosclerotic plaque pathology and the mechanisms of lipid-lowering therapy preventing ischemic events.

A.2. Study Design:

This project is a randomized open-label study.

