In this research project we will perform carotid MRI studies in 180 CAD patients with a family history of cardiovascular disease and ApoB ≥ 120 mg/dl (LDL-C levels 100-190 mg/dl). Fifty percent of these subjects will be women. The qualified subjects will be randomized to one of three treatment groups: (1) single therapy - atorvastatin alone; (2) double therapy – atorvastatin plus Niacin (2 g/day); (3) triple therapy – atorvastatin, Niacin plus ezetimibe (10 mg/day). . The treatment target for LDL-C will be ≤ 80 mg/dl for the single and double therapy groups and ≤ 60 mg/dl for the triple therapy group. The HDL-C target for two niacin-treated groups will be 10-12 mg/dl increase. All patients will undergo MRI examination of both carotid arteries annually for three years, a total of 4 examinations. If subjects are enrolled in the trial extension a “late time” scan may be performed at a median time of six years.

Following figure illustrates the study design.

*If subjects are enrolled in the trial extension a “late time” scan may be performed at a median time of six years.

In order to determine if carotid plaque characteristics predict future major cardiovascular events, we will ask the study participants who have completed the original 3-year protocol and carotid MRI examinations to continue on their randomized therapy for up to 11 more years. We will (a) continue to conduct clinical follow-up during the extension to collect cardiovascular events including fatal/non-fatal MI or stroke, hospitalization/revascularization for worsening ischemia, and mortality; (b) determine whether plaque characteristics (lipid content, volume and enhancement) at baseline and its change during therapy are statistically associated with cardiovascular events.

Duration: a mean of 5 years and maximum of 11 years

A.3. Primary Efficacy Parameters:

Primary endpoint: The primary endpoint of this study is carotid plaque lipid composition identified by MRI. The determination of plaque lipid content for each carotid artery will be performed using the automated interactive system. These measurements will be performed from the MRI scans at four time points blinded to time sequence of MRI examinations, patient treatment, lipid levels and clinical course.

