4. Risk of cardiovascular events: This set of analyses will focus on the risk of CV events in relation to plaque characteristics and the changes over time in the plaque. We will use methods of survival analysis (failure-time analysis) for this part of the study. We will use Kaplan-Meier plots, the log rank test and the Cox proportional hazards model for these analyses. The outcome variable is time to a first CV event during the study period, and those who do not have an event by the end of follow-up surveillance will be considered as censored. The two branches of this endeavor are (i) the relation of plaque volume and characteristics at one cross-sectional moment in time (such as baseline) to the risk of a subsequent event; and, (ii) the relationship between plaque “velocity”—the rate of change of plaque characteristics over time—to subsequent risk of an event. The velocity and cross-sectional status of plaque are two quite different biological concepts, and it may happen that one or the other alone, and not both, are important. For the first analysis, (i), each patient will have up to two time intervals: baseline to an event or to the 3-year MRI assessment, and then from the 3-year MRI assessment forward to the end of follow-up. By using two intervals per person, one initiated at baseline and the other initiated at 3 years, we will always be using the most recent MRI data on plaque status to compare to subsequent follow-up. This analysis is

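### No event follow-up is described for subjects who leave early, decline the extension or are removed, so Aim 5 loses events and may censor informatively

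*Combined protocol and SAP*

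**What the plan says.** Aim 5 (A.1) is to "determine whether plaque characteristics (lipid content, volume and enhancement) at baseline and its change during therapy are statistically associated with cardiovascular events", and it promises to "continue to conduct clinical follow-up for a median of 5 years" without limiting who is followed. A.3 likewise lists the cardiovascular events to be recorded, with no restriction.

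The sections that say how follow-up works after year 3 are narrower. In A.2, "we will ask the study participants who have completed the original 3-year protocol and carotid MRI examinations to continue on their randomized therapy", and the study will then "continue to conduct clinical follow-up during the extension to collect cardiovascular events". B.9 gives the four-monthly schedule: "Participants who complete the first 3 years of the study and are willing to continue on the randomized therapy and will be followed". A.2 therefore names three conditions (three years completed, MRIs completed, therapy continued) and B.9 names two, leaving out the MRIs.

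F.3.4 analyses time to first event. Analysis (i), on plaque status, starts at baseline and opens a second interval at the 3-year MRI. Analysis (ii), on plaque velocity, starts at the 3-year MRI. On censoring, the plan says that "those who do not have an event by the end of follow-up surveillance will be considered as censored". It has no rule for subjects who leave before that, and no sensitivity analysis for informative censoring.

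**The concern.** Whether baseline plaque predicts events can be answered for anyone with a baseline scan and known event status. Staying on the assigned drugs is not needed. Tying follow-up to it has two consequences.

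First, events are lost. The outcome is a first cardiovascular event in a study sized for 180 completers, with no event count or power stated for Aim 5, so each lost event matters.

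Second, censoring may be informative. Kaplan-Meier curves need censoring unrelated to later risk. The Cox model needs this given its covariates. The exits that the protocol itself describes have to do with tolerability and health: B.8 says niacin flushing can be hard to tolerate, C.3 has drugs reduced or stopped for laboratory findings, and D.2 removes subjects for renal decline with no event follow-up stated afterwards. Some of these could plausibly go with cardiovascular risk. If they also go with plaque, the estimated association could shift.

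**Working it through.** **Inputs from the documents.** A.4 gives up to 240 enrolled so that 180 complete. A.2 gives "Duration: a mean of 5 years and maximum of 11 years". B.9 runs visits to month 132, and 132/12 = 11 years. Both A.2 and B.9 also speak of up to 11 further years after year 3, or 14 in total. That conflict needs reconciling; horizons of 5 and 11 years are used here.

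**Assumptions (not in the documents).** 60 subjects leave evenly over years 0 to 3, a mean of 1.5 years each. A share q of the 180 completers, from 0 to 30%, declines the extension. Event rates are 2 to 5% per year. The hazard ratio is 1.4 per SD of plaque.

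**The plan's own figure.** 180/(1 − 0.25) = 240, so the enrolment ceiling allows for 60/240 = 25% non-completion. The 25% is solved backwards, because no dropout rate is stated.

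**Person-years** (potential follow-up to horizon T, not stopped at events). All followed: 240 × T. As described: 60 × 1.5 + 180(1 − q) × T + 180q × 3.

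| T | q | All followed | As described | Lost |
|---|---|---|---|---|
| 5 | 0 | 1200 | 90 + 900 = 990 | 17.5% |
| 5 | 30% | 1200 | 90 + 630 + 162 = 882 | 26.5% |
| 11 | 0 | 2640 | 90 + 1980 = 2070 | 21.6% |
| 11 | 30% | 2640 | 90 + 1386 + 162 = 1638 | 38.0% |

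**First events and power.** For a constant rate h, following everyone gives 240(1 − e^(−hT)). As described, the count is 60[1 − (1 − e^(−3h))/(3h)] + 180(1 − q)(1 − e^(−hT)) + 180q(1 − e^(−3h)). Power with D events is Φ(√D × ln 1.4 − 1.96). At h = 3%:

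| T | All followed | As described, q = 0 | As described, q = 30% |
|---|---|---|---|
| 5 | 33.4 events, 49% | 27.7 events, 43% | 24.8 events, 39% |
| 11 | 67.5 events, 79% | 53.2 events, 69% | 42.7 events, 59% |

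Over 2 to 5% per year at 5 years, events fall from 22.8–53.1 to 18.9–44.1 (q = 0) or 16.9–39.7 (q = 30%).

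**Is the loss informative?** The documents cannot say, so this was simulated: 60,000 subjects per scenario, 25% leaving early, a 3% baseline hazard, an unmeasured risk factor and a conditional hazard ratio of 1.4.

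- Leaving unrelated to risk: at 5 years 25% of subjects with and without events leave, and the hazard ratio is 1.38 with full follow-up against 1.39 observed.
- Leaving tied to plaque and the unmeasured factor: at 5 years 36 to 40% of subjects with an event leave, against 22 to 23% of those without. The hazard ratio goes from 1.39 to 1.37, or from 1.37 to 1.34 in the strongest case. At 11 years the strongest case goes from 1.37 to 1.31.
- Plaque association with leaving reversed: the hazard ratio moves up, from 1.35 to 1.39 at 5 years.

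The full-follow-up hazard ratio itself ranged from 1.35 to 1.39 across the 5-year scenarios, which differ only in who leaves. The 5-year shifts are thus close to simulation noise and should be read only as small.

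**The case against.** The strongest reply is that neither A.2 nor B.9 says that nobody else is followed. B.9 sets a visit schedule that includes drug dispensing, A.2 says who is invited to stay on therapy, and Aim 5 and A.3 state no limit. That is right as far as it goes: exclusivity is inferred from the lack of any other route. But A.2 places the later event collection inside the extension, and if everyone is meant to be followed, the text should say so.

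Several stronger readings are tempting and not supported:

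- A reader might infer that Aim 5 loses events unevenly. Nothing in the documents shows who leaves, by arm, plaque or risk. Aim 5 compares no arms, so unequal leaving between arms biases it only if leaving is also tied to plaque or to risk beyond the model covariates.
- A reader might infer that stopping niacin ends follow-up. The protocol builds niacin reduction and interruption into the regimen, and such a subject may still be willing to continue. Whether that counts as continuing randomised therapy is not stated.
- A reader might take 25 to 40% of events as lost. The formula 60r/(60r + 180) gives 25%, 33% and 40% for assumed rate ratios r of 1, 1.5 and 2, but for post-year-3 events only and with all 60 alive and event-free at year 3. For all events over 5 years at low rates, 60r × 3.5/(60r × 5 + 180 × 5) gives 17.5%, 23% and 28%. First events before leaving are kept.
- The A.2 and B.9 difference might be read as two policies. It may be wording only, since annual MRIs belong to the 3-year protocol. It still matters for a subject who can no longer be scanned.

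It also stands that analysis (ii) needs the 3-year MRI by construction. The avoidable restriction there is continued therapy.

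**Conclusion.** The concern holds in a limited form. As written, post-year-3 event follow-up reaches three-year completers who stay on randomised therapy, and no route is described for anyone else. For the baseline-plaque analysis this restriction serves no purpose.

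The loss of events follows from any positive event rate. Its size rests on A.4's ceiling of 60 leavers and on the assumed timing of leaving: about 17.5% of person-years at 5 years and 22% at 11 years, or up to 26.5% and 38.0% if 30% of completers decline. Fewer leavers would mean a smaller loss.

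Informative censoring is a risk that the plan does not examine, not a demonstrated bias. Neither its size nor its direction can be had from the documents, and the simulated shifts were small at 5 years and larger at 11. The change is worth making because it is cheap, recovers events and reduces exposure to that risk.

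**What to change.** **A.2 and B.9.** Separate event follow-up from study drug and MRI completion, and use one eligibility wording in both. Seek consent from every randomised subject, including those who left, declined the extension or were removed, for event and vital-status follow-up by telephone and record check to the end of surveillance. The rules on stopping drug or removing subjects need not change.

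**F.3.4, analysis (i).** Include all randomised subjects with a baseline scan. Where the 3-year scan is missing, use the latest available scan as the time-varying plaque value; this ages the measurement, and the report should say so. Censor at last known event status. Report numbers and reasons for leaving by arm and by baseline plaque. Add a sensitivity analysis with inverse-probability-of-censoring weights, which addresses measured predictors of leaving only. Censoring at the end of therapy would not do this job, because it adds therapy-related censoring.

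**F.3.4, analysis (ii).** Include everyone with a 3-year MRI, whether or not they continue therapy.

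**Cost.** A protocol and consent amendment, and periodic calls by existing coordinators to about 60 subjects at A.4's ceiling, plus completers who decline. Some will refuse or not be found. No extra visits, scans or drug are needed.
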